**Table 4. Power Calculations**

Aim	Respondents/Source	Measure	N per group	Detectable Effects with 80% power
1a	PCPs	Changes in Comfort and Competence in addressing CM	137	Effect size  of 0.42
1a	Parents	Parent satisfaction	144	Effect size  of 0.41
1b	Staff	Staff Perceptions	24/72 	Effect size  of 0.82
2	Practices	Proportion adopting	59	Precision of +/- 15 pct points
3	EHR	Pre-post prevalence of CM-related diagnoses	98,000	5% vs. 4.5%  10% vs. 9.6%

Defined as the difference in means between groups divided by the standard deviation.

Conservatively assuming an imbalance between SEEKonline vs. Traditional of as much as 25% to 75%.

In our previous evaluations of SEEK, we observed rates of CM in the medical record ranging from 5% to 1%.

methods.

**Qualitative/Mixed Methods Analysis.** An audit trail of data collected and memos, team meetings indicating time, place, source of data, and persons collecting or analyzing information, will be kept. Procedures for data collection and the role of the investigator collecting the data will be detailed and reviewed with each member of the research team. We will analyze interview transcripts using a thematic content analysis methodology. First, transcripts will be distributed among investigators. Each will review these to develop a broad understanding of content related to the project's aims and to identify topics for discussion and observation. During this and subsequent steps, investigators will prepare short descriptive statements or "memos" to document initial impressions of topics and themes and their relationships, and to define the boundaries of specific codes (i.e., the inclusion and exclusion criteria for assigning a specific code). Second, transcripts will be independently coded to condense the data into analyzable units. Segments of text ranging from a phrase to several paragraphs will be assigned codes based on a priori (i.e., from the interview guide) or emergent themes (or, open coding). Codes will be assigned to describe connections between categories and between categories and subcategories (i.e., axial coding). Codes will also be assigned to reflect the social and demographic characteristics of study participants. Lists of codes developed by each investigator will be matched and integrated into a single codebook. Third, each text will be independently coded by at least two investigators. Disagreements in assignment or description of codes will be resolved through discussion

**Cost Analysis.** We will conduct cost effectiveness analyses taking the perspective of a practice. Total practice cost of implementation will be calculated for both training arms (IND and MOC). Cost effectiveness ratios will be calculated as the cost per average SIC component completed, and per average Competence scale and Practice Behavior scale scores. Standard time discounting methods will be applied to cost estimates. We will use sensitivity analyses to derive upper and lower estimates of resource use and intervention costs. Standard errors for use in mean comparisons will be estimated, using bootstrapping

between investigators and by refining definitions of codes. The final list of codes or codebook, constructed through team consensus, will consist of a numbered list of themes, issues, accounts of behaviors, and opinions that relate to evidence use and its determinants. With the final coding structure, two investigators will separately review transcripts to determine level of agreement in the codes. A level of agreement ranging from 66-97% depending on level of coding (general, intermediate, specific), indicates good reliability in qualitative research. Fourth, based on these codes, the computer program QSR NVivo will generate a series of categories arranged in a treelike structure connecting text segments grouped into separate categories of codes or “nodes.” These nodes and trees will be used to further the process of axial or pattern coding to examine the association between different a priori and emergent categories. They will also be used in selective coding of material to identify the existence of new, previously unrecognized categories. The number of times these categories occur together, either as duplicate codes assigned to the same text or as codes assigned to adjacent texts in the same conversation, will be recorded, and specific examples of co-occurrence illustrated with transcript texts. Fifth, by constantly comparing these categories with each other, the different categories will be further condensed into broad themes using a format that places SEEK’s effectiveness and implementation within the framework of the system characteristics. Finally, the theme will be compared with the results of the analysis of quantitative data relating to PCP experiences specific to SEEK and its implementation to identify points of convergence and divergence (triangulation) and to explain or account for potentially unanticipated findings (expansion).

**Sample Size Considerations.** Since this qualitative analysis involves no hypothesis testing using statistical procedures, the number of subjects necessary to produce sufficiently valid and reliable results cannot be calculated using standard formulas for statistical analysis. Nevertheless, previous studies relying upon this methodology have typically found that information becomes repetitive with little new information gained after analyses of data from 20-30 participants. Some authors suggest that saturation can be achieved with as few as 12 respondents. By this standard, we should have an adequate sample to assess feasibility and acceptability and to identify potential barriers to and facilitators of implementing SEEK.

**Study Limitations.** First, we considered randomizing SEEKonline vs. the Traditional approach, but think this may be difficult for some practices. Nevertheless, we will be able to compare outcomes related to these approaches, and, we are positioned to assess this intervention in real world circumstances. Second, while SEEK originally included a social worker, the core element was a means of facilitating referrals to community resources – often done by a PCP and office staff, and that remains. We think the “what” gets done is more important than the “who.” We will be able to qualitatively assess the role of behavioral health; the numbers however preclude doing so quantitatively. Third, medical records clearly offer only a partial view of possible CM, although they are a means of detecting abuse and neglect that may not be reported to CPS. Given the multiple regions and logistics of this study, gathering CPS and parental self-report data on CM are not feasible.

**Summary.** This innovative hybrid III implementation trial examines two technology driven implementation strategies to scale-up SEEK in primary care practices. Using technology to facilitate quality training and service delivery of the SEEK model has the potential to increase efficiency and acceptability. Understanding how to best implement SEEK should enhance primary care in both pediatric and family medicine settings by better addressing prevalent psychosocial problems. Doing so can improve the wellbeing of families and parents and thereby promote children’s health, development and safety, and help prevent CM. Outcomes can provide valuable lessons for other implementation efforts that address social determinants of child health problems.

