## A. SIGNIFICANCE

**Prevalence.** Child maltreatment (CM) is a major public health problem in the US, affecting many lives, in the short-and long-term, and costing individuals, families and our society dearly. In 2015, 7.2 million children were reported to Child Protective Services (CPS). Of these, 683,000 children (i.e., 9.2 per 1000) were “substantiated” victims of child abuse and neglect. Yet, reported cases capture only the tip of the iceberg. The National Incidence Study (NIS-4), using observations by community professionals, estimated that 1.26 million children (i.e., 17.1 per 1,000) were maltreated in 2005-06, and the more inclusive “Endangerment Standard” estimated nearly 3 million victims (i.e., 40 per 1,000). **Outcomes.** The consequences of CM can be devastating - in the short- and long-term. In addition to injuries and physical health problems, child and adolescent sequelae include many psychological and behavioral problems. CM has also been linked to an array of adult outcomes such as substance use disorders, HIV/AIDS-related sexual risk behaviors and being a victim and/or perpetrator of intimate partner violence (IPV). Other problems in adulthood include depression, suicide, criminal behavior, interpersonal problems, and academic and vocational difficulties, as well as multiple physical health problems. **Costs.** The financial costs of CM are immense. The costs associated with injuries due to physical abuse far exceed the per-child costs of non-inflicted injuries of comparable severity. Two-thirds of the medical costs of CM are paid through Medicaid. Additional costs are incurred by the child welfare, educational, mental health, and judicial systems, with estimated U.S. costs of \$103.8 billion per year. The human and economic costs of CM point to the serious need for effective preventive strategies, and the broad implementation of evidence-based practices (EBPs).

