### Studies' Findings

**Impact on PCPs.** In both studies, PCPs in SEEK practices reported significantly greater comfort and perceived competence in addressing the targeted risk factors, compared to controls. Improvements were sustained for 18-36 months. Review of medical records revealed that PCPs in SEEK practices were significantly more likely than controls to screen for the targeted risk factors for CM. In SEEK II, this was confirmed by direct observation; screening increased on average across practices from less than 5% to 62% of visits. In SEEK I, parents in SEEK clinics reported more favorable views of their child's PCP. Importantly, busy PCPs demonstrated they could effectively implement SEEK.

**Impact on CM.** Three measures from three sources assessed CM: 1) parent self-report on the Conflict Tactics Scale, 2) review of children's medical records for abuse or neglect, and 3) CPS reports. *Parent self-report.* SEEK I parents reported fewer "severe physical assaults" than controls (0.11 vs. 0.33,  $p = .04$ ). SEEK II parents reported fewer instances of Psychological Aggression ( $p = .02$ ) and Minor Physical Assaults ( $p < .05$ ) than did controls. *Medical records.* Children in SEEK I practices had less medical neglect than did controls. There was less "non-compliance" with medical care (4.6% vs. 8.4%,  $p = 0.05$ ), and fewer delayed immunizations (3.3% vs. 9.6%,  $p = 0.002$ ). *CPS reports.* In SEEK I, fewer families were reported to CPS (12% vs. 19.7%,  $p = .04$ ). A report was prevented in one of every 13 such families exposed to SEEK.

**Time Required.** SEEK did not require significantly more time, on average, for PCPs to address psychosocial problems. Parents completing the PQ before visits saved time; this was offset when addressing problems.

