nested within practices which are nested within the 5 healthcare systems. The participating systems will be randomized to one of two start times - 9 or 16 months from project start date, beginning with one pediatric and one family medicine system (cohort 1). Staggering the start time addresses the capacity limitations of the training and research staff.

**Sample.** We will offer SEEK to the 5 healthcare systems. Inclusionary criteria are: 1) practices not already implementing SEEK, 2) practices providing primary care to children, and 3) agreement to participate. The systems have indicated a general commitment to this project; they include 59 practices with 306 PCPs. Our recruitment efforts in SEEK II were very successful with 75% (18/24) of practices agreeing to participate, including all the PCPs in those practices. We plan to study 13 pediatric and 35 family medicine practices. If more practices are interested, we will select the first 48 choosing to participate. In the unlikely event that fewer than 48 are interested, we will approach other healthcare systems. In addition to 5 system leaders, we will recruit 5 groups of participants: 1) all 48 practice leaders, 2) 275 PCPs, 3) 16 behavioral health professionals, 4) 96 ancillary staff, and 5) 288 parents (6 per practice). These estimates are based on current staffing. Smaller subsamples will be purposively selected for qualitative interviews according to practice type, training strategy and presence of integrated behavioral health.

We will also request limited consent from practice leaders and PCPs who opt out to briefly probe their decision. We will ascertain aggregated ICD-10CM-related diagnoses on all children 0-5 attending the practices (N~90,000). Based on our experience, we anticipate 60% of practice leaders and PCPs will be female as will be most of the other participants. Different regions provide diversity in terms of urban, suburban and rural locations, and racial/ethnic diversity (e.g., 2 systems serve a predominantly Latino population). Three systems have integrated behavioral health professionals. These contextual factors will be considered in all analyses.

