**Aim 3. Examine the effectiveness of SEEK in reducing CM.** As in our previous studies, we will identify CM-related diagnoses, now via EHRs. We will review the EHR for each child (0-5) in each practice for two years prior to implementing SEEK and during implementation. The presence of CM-related ICD-10 codes will be recorded. The proportion of children with CM diagnoses before and during SEEK will be compared at each practice. Formal inference regarding the best estimate and statistical significance of pre-post differences will be based on a binary regression model with a random effect for site, similarly to Aim 1.

**Sample Size Considerations.** Our projected sample sizes (numbers of practices, professionals within each practice, and children in the practices) should provide good precision to estimate parameters and ample power to detect moderate associations. Table 4 below shows the detectable effect sizes for various comparisons, based on performing 2-sided .05-level tests and incorporate a 1.5-fold increase in variance and sample size to account for potential loss of power due to clustering of observations within practices and systems. In general, the detectable effect sizes are moderate, at plausible levels. We observed effect sizes of about 1.0 regarding Competence and Comfort in SEEK II. For Aim 2, assuming 90% of practices provide organizational information, we will estimate the rate of adoption of SEEK accurately,  $\pm$  15 percentage points.

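### Table 4 and its footnote 3 disagree on the base rate behind the Aim 3 detectable effects, and the two printed pairs do not follow from the plan's own method

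*Combined protocol and SAP*

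**What the plan says.** The Aim 3 row of Table 4 is labelled "Pre-post prevalence of CM-related diagnoses". It gives 98,000 per group and lists two detectable pairs, 5% against 4.5% and 10% against 9.6%, under the column "Detectable Effects with 80% power". Footnote 3, attached to the first pair, reads "we observed rates of CM in the medical record ranging from 5% to 1" percent.

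The Sample Size Considerations paragraph of the Data Analysis Plan says the table is "based on performing 2-sided .05-level tests", and that the calculations "incorporate a 1.5-fold increase in variance and sample size to account for potential loss of power due to clustering". It describes the detectable effects as moderate and plausible.

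Three other places bear on the base rate or the sample size:

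- Studies' Findings gives medical-record results from the first SEEK trial: non-compliance with care at 4.6% against 8.4%, and "fewer delayed immunizations (3.3% vs. 9.6" percent. Both are reported as medical neglect.
- The Significance section gives population figures, including "683,000 children (i.e., 9.2 per 1000" for substantiated maltreatment, and 17.1 and 40 per 1,000 from a national incidence study.
- The Sample paragraph describes "all children 0-5 attending the practices (N~90,000", where Table 4 has 98,000.

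**The concern.** A detectable difference between two proportions depends on the base rate, and a footnote citing observed rates is there to justify the base rates chosen. Here it does not. Read as printed, the observed range has 5% as its upper end. One of the two scenarios is then twice the highest observed rate, and nothing is shown for the rest of the range.

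This matters because, for a fixed number of children, the detectable absolute difference shrinks as the base rate falls but the detectable relative reduction grows. The printed pairs are relative reductions of 10% (0.5/5) and 4% (0.4/10). If the true rate were near 1%, neither would indicate what Aim 3 can detect, and a null result would be hard to interpret.

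**Working it through.** **Inputs.** Two-sided alpha 0.05 and the 1.5-fold clustering factor come from Sample Size Considerations. Power of 80% and 98,000 per group come from Table 4. Taking the groups as the two periods, of equal size and independent, is an assumption.

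**Reading the 1.5 factor.** Dividing each group size by 1.5 and using a two-sample t-test reproduces the other rows of Table 4:

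- 137/1.5 = 91.3 gives an effect size of 0.417 (printed 0.42).
- 144/1.5 = 96 gives 0.406 (printed 0.41).
- 24/1.5 = 16 and 72/1.5 = 48 give 0.822 (printed 0.82).

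This is therefore the plan's method. For Aim 3, n = 98,000/1.5 = 65,333 per period.

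**Formulas**, with q = 1 − p:

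- Standard error: SE = √[(p1q1 + p2q2)/n]
- Power ≈ Φ[(p1 − p2)/SE − 1.960]
- Detectable difference at 80% power: p1 − p2 = (1.960 + 0.842) × SE, solved for p2

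**The printed pairs**

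- 10% against 9.6%: SE = √[(0.0900 + 0.0868)/65,333] = 0.001645. The ratio is 0.004/0.001645 = 2.432, so power = Φ(0.472) = 68%. Reaching 80% needs about 130,100 per period.
- 5% against 4.5%: SE = √[(0.0475 + 0.0430)/65,333] = 0.001177. The ratio is 0.005/0.001177 = 4.249, so power = Φ(2.289) = 99%. About 42,600 per period would give 80%.

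One row is optimistic and the other conservative, and no single variant tried reproduces both. The 10% pair matches if the 1.5 factor is left out (9.62%) or the test is one-sided (9.59%). The 5% pair matches if 98,000 is the total over both periods, 49,000 each with the 1.5 factor (4.53%).

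**Detectable values by the plan's method**

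| Base rate | Detectable rate | Absolute difference (points) | Relative reduction | Power for a 10% relative reduction |
|---|---|---|---|---|
| 10% | 9.54% | 0.46 | 4.6% | >99% |
| 5% | 4.67% | 0.33 | 6.6% | 99% |
| 3% | 2.74% | 0.26 | 8.6% | 90% |
| 2% | 1.79% | 0.21 | 10.6% | 75% |
| 1% | 0.85% | 0.15 | 14.8% | 46% |

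Example for the last column: 1% against 0.9% has SE = √[(0.0099 + 0.008919)/65,333] = 0.000537. The ratio is 0.001/0.000537 = 1.863, so power = Φ(−0.097) = 46%. Reaching 80% would need about 221,600 children per period.

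**Sensitivity to the number of children.** With 90,000 per period (60,000 after the factor), the detectable rates are 9.52%, 4.65%, 1.78% and 0.845% at base rates of 10%, 5%, 2% and 1%. Power for 1% against 0.9% is 43%. The pattern is unchanged.

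**The case against.** The strongest reply is that 1% is a dropped zero. The range is printed in descending order, the scenarios are exactly 5% and 10%, and the first SEEK trial's record-based rates (3.3% to 9.6%) fit a 5% to 10% range better than a 1% to 5% one. If so, most of the base-rate gap disappears. This reading is plausible, but the documents do not confirm it. The footnote would still need correcting, and the two pairs would still not follow from one calculation. Even as printed, 5% is inside the range, so one plausible base rate is covered.

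A reader might infer three stronger things, none of which the documents support.

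- *That the 3.3% to 9.6% rates are irrelevant because they are neglect indicators rather than maltreatment diagnoses.* The plan treats medical-record neglect as one of its maltreatment measures and says Aim 3 follows the earlier studies. It gives no ICD-10 code list, so nothing shows that neglect is excluded.
- *That the population figures put the true rate near 1%.* They are a different measure, are not limited to ages 0 to 5, and do not accumulate over a two-year baseline and the implementation period. They also cut both ways. Dividing 683,000 by 0.0092 gives about 74 million children, so 7.2 million reported is roughly 9.7%. Reports are not diagnoses either.
- *That Aim 3 would miss its effect.* Each printed pair is conditional on its own base rate, and the plan never claims a 4% or 10% relative change at 1%. At 5% the design does better than the table says. At 1% it still detects about a 15% relative fall. The first SEEK trial's difference in protective-services reports was (19.7 − 12)/19.7 = 39% relative. A fall of that size from 1% would have over 99% power under these inputs, though it is a different outcome in a different population.

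**Conclusion.** The table and its footnote disagree as printed, and the documents do not say which is right. By the plan's own method the Aim 3 row should read 10% against 9.54% and 5% against 4.67%. The printed 10% pair has about 68% power rather than 80%, and the printed 5% pair about 99%. If the low end of the footnote is real, the detectable reduction rises to 10.6% relative at 2% and 14.8% at 1%.

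This is a shortfall in the stated justification. It does not show that Aim 3 is underpowered. The figures assume two independent periods of equal size and accept the 1.5 factor. The documents give no intraclass correlation to check that factor, although there would be about 2,000 children per practice (98,000/48), so the decimals should not be over-read.

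**What to change.** - Confirm or correct the range in footnote 3.
- Restate the Aim 3 entries as 10% against 9.54% and 5% against 4.67%, from one stated calculation.
- If 1% is meant, add 2% against 1.79% (10.6% relative) and 1% against 0.85% (14.8% relative). Note that a 10% relative reduction has about 75% power at 2% and 46% at 1%.
- State that the base rate refers to the same set of maltreatment-related ICD-10 codes that Aim 3 will count.
- While the row is open, use one figure for the number of children in Table 4 and the Sample paragraph, and rerun the row if it is not 98,000.

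The cost is one footnote, one revised row and up to two added entries, with no change to design, data collection or analysis. The only downside is a slightly less favourable stated figure at 10% and at low base rates; the figure at 5% improves.

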**Table 1. SEEK Training Strategies**

SEEK MOC-4	Independent Online (IND)
Eligible for MOC 4 and CME credits	Eligible for MOC CME credits
Engage in SEEK QI project – PDSA cycle	N/A
Participate in four 1-hr. webinars	N/A
View SEEK training videos (2.5 hours)	View SEEK training videos
Pass SEEK Post-test	Pass SEEK Post-test
Participate in 3 one-hour consultation sessions	Participate in 3 one-hour consultation sessions

**Facilitation of Service Delivery.** SEEKonline is software to efficiently implement SEEK via a secure web-based system interfacing with a practice's EHR. SEEKonline has been developed and is currently being beta tested. Its effectiveness in improving implementation outcomes compared to the Traditional paper-and-pencil approach has yet to be examined. Data are stored in a Microsoft SQL Server Database, in an isolated, secure, private cloud environment, behind a fully HIPAA-certified network security device. SEEKonline enables parents to privately complete the SEEK PQ before a child's checkup. Responses are available to PCPs

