### **Organizational Assessment**

Organizational measures will be administered at baseline regarding the opportunity to adopt SEEK. Practice leaders and PCPs who decide to participate in the study will be recruited; those who opt out will be asked to complete the one-time brief online SEEK Adoption Survey and the following 4 measures. A subsample will undergo a semi-structured, 30-minute phone interview.

**Demographics Form.** This includes the healthcare system and practice structure, annual budget, number of practices, number and characteristics of PCPs, presence of behavioral health and patient demographics.

**Evidence-Based Practice Attitude Scales (EBPAS).** The 15-item EBPAS measures 4 domains of service providers' attitudes toward adopting EBPs: *appeal* (the extent to which one would adopt an EBP if it is appealing), *requirements* (willingness to adopt an EBP if required to do so), *openness* (general openness to new interventions), and *divergence* (the degree to which one believes that EBPs are less important than clinical experience). Subscales have adequate internal consistency (Cronbach's  $\alpha = .67\text{-.91}$ ) and convergent validity.

**Implementation Leadership Scale (ILS).** The 12-item ILS assesses leader support for EBPs within an organization (5-point Likert scale). Four subscales - *proactive*, *knowledgeable*, *supportive*, and *perseverant* leadership - have excellent internal consistency ( $\alpha = .95$  to  $.96$ ), and convergent and discriminant validity.

**Implementation Climate Scale (ICS).** The 18-item ICS assesses how the organization views new interventions. Implementation climate is defined as shared perceptions of policies, practices, procedures and behaviors that are rewarded, expected and supported. The measure has strong psychometrics with internal consistency ( $\alpha = .81\text{-.91}$ ), convergent validity, and validation in a sample of child welfare professionals.

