## **Measuring Costs**

The cost analysis will provide estimates of the overall practice-level costs associated with implementing SEEK. Cost measurement will be organized using the Cost of Implementing New Strategies (COINS) framework which provides a structure for measuring and categorizing costs. Implementation costs include all resources used to deliver SEEK. COINS maps onto the SIC, by tracking the costs and resources needed to complete each implementation activity. In SEEK II, PCPs in the intervention arm did not require more time per child than did controls. It seems reasonable to apply this to the current study, rather than conduct another time study.

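### The MOC versus IND cost comparison states no adjustment for practice size, which gives up precision and lets chance size imbalance into the cost difference and ratios

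*Combined protocol and SAP*

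**What the plan says.** The Cost Analysis paragraph of the Data Analysis Plan sets the outcome: "Total practice cost of implementation will be calculated for both training arms (IND and MOC"). It then forms the ratios: "Cost effectiveness ratios will be calculated as the cost per average SIC component completed, and per average Competence scale and Practice Behavior scale scores". On inference it says "Standard errors for use in mean comparisons will be estimated, using bootstrapping" methods. No covariate, offset or per-PCP cost is named. Measuring Costs confirms the level: "The cost analysis will provide estimates of the overall practice-level costs associated with implementing SEEK", and counts every resource used in delivery.

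Other parts of the document bear on practice size:

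- **Organizational Assessment.** The Demographics Form, among measures taken at baseline, records "number and characteristics of PCPs, presence of behavioral health and patient demographics".
- **Table 1.** Both arms have 2.5 hours of videos and three one-hour consultations. Only MOC has the Plan-Do-Study-Act (PDSA) project and the line "Participate in four 1-hr. webinars".
- **Procedures, Implementation Phase.** Practices are randomised within practice type (pediatric or family medicine). Size is not a stratum.
- **Sample.** 48 practices and 275 PCPs are planned, from a pool of 59 practices and 306 PCPs. The contextual factors promised for every analysis follow a passage on region, urban or rural location, race/ethnicity and behavioral health. Practice size is not among them.
- **General Considerations.** Random effects for system and practice deal with clustering. They do not remove variation due to size from a single total per practice.

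**The concern.** A practice's total cost rises with its number of PCPs, because videos, consultations, webinars and the PDSA project all take PCP time. Differences in size therefore add variance to each arm's mean cost, and a known baseline variable could remove much of it. Since randomisation does not balance size, one arm may by chance hold larger practices. Its mean cost then moves for a reason unrelated to training.

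Two of the ratios inherit the problem. Average Competence and Practice Behavior scores do not grow with the number of PCPs, but the total cost above them does. As an illustration with assumed sizes, take two IND practices of 3 and 9 PCPs with the same scores. Their training time is 3 × 5.5 = 16.5 h and 9 × 5.5 = 49.5 h, a threefold difference in the ratio at identical cost per PCP.

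The economic consequences of each training strategy are part of Aim 2, so the precision of this contrast matters.

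**Working it through.** **Figure to reproduce.** There is none. Table 4 has no cost row, and the documents give no cost SD, expected cost difference or spread of practice size.

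**Inputs from the documents.** Documented hours per PCP are 2.5 + 3 = 5.5 for IND and 5.5 + 4 = 9.5 for MOC. PDSA time is not given and is set to 0. Mean size is 275/48 = 5.73 PCPs (planned) or 306/59 = 5.19 (pool).

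**Assumed inputs.** 24 practices per arm; CV of practice size; residual cost CV; other implementation time. Costs are in PCP hours.

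**Step 1: chance imbalance in mean size.** The SE of the arm difference, relative to the mean, is CV × √(2/24).

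| Size CV | SE of imbalance |
|---|---|
| 0.4 | 12% |
| 0.6 | 17% |
| 0.8 | 23% |

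For scale, the MOC/IND ratio of documented training hours is 9.5/5.5 = 1.73. With an assumed 6 further common hours per PCP and 30 fixed hours per practice, it is (30 + 5.19 × 15.5)/(30 + 5.19 × 11.5) = 110.4/89.7 = 1.23.

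**Step 2: analytic standard error.** Take cost = PCPs × hours per PCP × residual, with mean size m = 5.73, size CV 0.5 and residual CV r = 0.3. The difference is 4 × 5.73 = 22.9 h per practice.

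- SE on totals = m × √{[(1 + CV²)(1 + r²) − 1] × (h_IND² + h_MOC²)/24}
- SE on cost per PCP = r × √{(h_IND² + h_MOC²)/24}
- Power = Φ(difference/SE − 1.96)

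Training hours only:

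- Totals: 5.73 × √(0.3625 × 120.5/24) = 7.7 h; power 0.84.
- Per PCP: 0.3 × √(120.5/24) = 0.67 h against a difference of 4 h; power 1.00.

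With 5.5 further common hours per PCP (11 and 15 h):

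- Totals: 5.73 × √(0.3625 × 346/24) = 13.1 h; power 0.42.
- Per PCP: 0.3 × √(346/24) = 1.14 h; power 0.94.

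**Step 3: simulation of the regression.** Lognormal size with mean 5.19, so the difference is 4 × 5.19 = 20.8 h. A comparison of unadjusted means is set against a regression on arm and number of PCPs. At size CV 0.6 and residual CV 0.2:

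| Cost included | SE unadjusted | SE adjusted | Reduction |
|---|---|---|---|
| Training hours only | 7.4 h | 3.3 h | 1 − 3.3/7.4 = 55% |
| Plus 6 h per PCP and 30 h per practice | 13.7 h | 6.7 h | 1 − 6.7/13.7 = 51% |

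Over size CVs of 0.4 to 0.8 and residual CVs of 0.2 to 0.4, these two cost structures gave reductions of roughly 20 to 60%. The smallest came with high residual variation and little spread in size. A cost that is mostly fixed per practice would gain less.

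**Step 4: sensitivity of the size of the problem.** In the second structure, an assumed 4 h of PDSA time per PCP lifts unadjusted power from 31% to 76%. Raising the residual CV to 0.4 instead leaves power at about 23% unadjusted and 35% adjusted.

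**The case against.** Several points on the other side have force.

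- **The plan does not say the comparison is unadjusted.** It only fails to state an adjustment, and the analysis section says it covers the main analyses. Aim 1b lists costs among outcomes for regression, but for SEEKonline versus Traditional. Aim 2 plans regression on practice characteristics, but for SIC measures. Neither covers MOC versus IND cost. The omission stands, but it is an omission and not a stated method.
- **A reader might infer that size variation swamps the training cost difference.** The documents do not support that. The spread of size and the cost SD are assumed, and PDSA time, counted as zero here, would widen the difference. Nor does adjustment rescue every case, as Step 4 shows.
- **A reader might also infer bias.** Practices are randomised, so the consequence is lost precision and chance imbalance. That larger practices look costlier per score point under either training does not favour an arm.
- **Cost has no hypothesis test.** That is true, so the standard error is the better yardstick and power only an illustration.
- **The analysis deliberately takes the practice's perspective.** SIC is measured on practices, so practice cost per SIC component is coherent. The scale mismatch is confined to the Competence and Practice Behavior ratios.
- **The size variable may not be ready to use.** Table 3 calls the form system demographics and names system leaders as respondents. PCP participation is voluntary, so a count of participants made after assignment could be affected by the arm.

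**Conclusion.** The point holds as a matter of precision. The plan states no size adjustment for the MOC versus IND cost comparison, although a baseline size variable is planned and much of the documented cost scales with it. The gain from using it is a reduction in standard error of roughly 20 to 60%. That range rests on 24 practices per arm, size CVs of 0.4 to 0.8, residual CVs of 0.2 to 0.4 and the two cost structures examined. Every one of these except the documented training hours and mean practice size is assumed. A chance size imbalance of 12 to 23% of the mean (one SE) would pass almost fully into the cost ratio where cost is proportional to size, and less where part of it is fixed. The finding shows neither a biased comparison nor one that is bound to fail.

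**What to change.** In the Cost Analysis, estimate the MOC–IND difference by regressing practice cost on arm, practice type and the number of PCPs in the practice, with that count fixed before randomisation. Bootstrap practices within arm for the standard error.

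For the Competence and Practice Behavior ratios, also report cost per PCP using the same pre-randomisation count, not participation after assignment. Keep total practice cost for the SIC ratio and as the descriptive summary from the practice's perspective.

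Confirm that PCP counts are held for each practice and not only for each system. Fix their date as well: Table 3 puts baseline for the first cohort at month 8, while Procedures puts its randomisation in month 5. The planned sample is based on current staffing, so a count at recruitment should be obtainable.

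The cost is a few sentences and a little more analysis, with no new data if counts per practice exist. The small downside is that the adjusted difference describes practices of a given size, so the unadjusted total should be shown beside it.
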